5.6. PATIENT REGISTRATION

After ensuring that the patient meets all eligibility criteria and the patient or his/her representative has given written informed consent, he/she will be entered into the trial by contacting the clinical trial monitor designated by the Sponsor(s) and faxing the completed Patient Registration Form (Fast Fact Sheet). The Sponsor(s) will check this Registration Form and confirm eligibility. A patient number will be provided to the site of enrolment within one working day. This patient number should be used on all future documentation and correspondence referred to this patient.

5.7. EVALUATIONS DURING TREATMENT

The following assessments will be done while the patient is on treatment ([Table 6](#)). A 2-day window is allowed for the different tests and procedures (except where otherwise specified).

Table 6. Evaluations during treatment

	ASSESSMENT	TIME
1. Clinical examination	• Complete physical examination. • ECOG PS (Appendix 1).	Day 1 of Cycle 1 prior to the Zalypsis® infusion, and then whenever clinically indicated.
	• Vital signs: heart rate, blood pressure and body temperature.	Before any Zalypsis® infusion.
	• Weight and BSA.	Repeat on Day 1 of each cycle prior to the Zalypsis® infusion, and then whenever clinically indicated.
	• Concomitant disease and treatments.	Throughout the “on-treatment” period*.
2. Laboratory tests	• Hematology: differential WBC (neutrophils, lymphocytes), hemoglobin and platelets. • Biochemistry A: liver function tests (ALT, AP, AST, LDH, total bilirubin), creatinine, CPK, troponin I**, glucose, and serum electrolytes (Na ⁺ , Cl ⁻ , K ⁺ , Ca ⁺⁺ , Mg ⁺⁺).	Repeat on Days 1, 8 and 15 of each cycle prior to Zalypsis® infusion. If NCI-CTCAE grade ≥ 3 occurs, the appropriate test(s) should be repeated at least every 2-3 days until recovery to grade ≤ 1 or baseline. In case of febrile neutropenia (any grade) ANC determination must be repeated every day until resolution.
	• Biochemistry B: total protein and albumin.	Repeat on Day 1 of each cycle prior to Zalypsis® infusion, and then whenever clinically indicated. If NCI-CTCAE grade ≥ 3 occurs, the appropriate test(s) should be repeated at least every 2-3 days until recovery to grade ≤ 1 or baseline.
3. Calculated creatinine clearance	Calculated according to Cockcroft and Gault's formula (Appendix 4).	Repeat on Day 1 of each cycle prior to the Zalypsis® infusion, and then whenever clinically indicated.
4. ECG**		ECG must be repeated prior to administration of each Zalypsis® infusion and if clinically indicated.
5. LVEF**	ECHO.	Repeat every other cycle, with a 1-week window, and if clinically indicated.
6. Pregnancy test, if applicable		Every four weeks during treatment and three months after last Zalypsis® administration.

	ASSESSMENT	TIME
7. AEs	As per NCI-CTCAE v. 4.0.	Throughout the “on-treatment” period*. Patients withdrawn with Zalypsis®-related ongoing AEs must be followed up with the appropriate tests until event resolution.
8. Tumor Assessment	CT-scan or MRI of all evaluable sites of disease, as per RECIST v. 1.1.	Every other cycle (\pm 1 week) until PD.
9. PK samples	See Section 6 .	Blood samples will be collected on Day 1 and 8 of Cycle 1, two before Zalypsis® end of infusion and six thereafter, at 30 min, 2 h, 6 h, 24 h, 48 h and 168 h after end of infusion.
10. Pharmacodynamic samples, from consenting patients	See Section 8.4 .	On Day 1 before each Zalypsis® infusion for the first six cycles, and every three cycles thereafter.
11. Other tests		When indicated, according to the clinical and laboratory context.

*On-treatment period = from first infusion of Zalypsis® to End of treatment.

End of treatment = 30 days after the day of last dose of study drug administration, unless the patient starts a new antitumor therapy or dies (whichever occurs first), in which case the date of administration of this new therapy or the date of death will be considered the date of end of treatment.

** All troponin I determinations, ECGs and LVEFs will be reviewed by external cardiologists.

ALT, alanine aminotransferase; AP, alkaline phosphatase; AST, aspartate aminotransferase; BSA, body surface area; CPK, creatine phosphokinase; CT, computed tomography; ECG, electrocardiogram; ECHO, echocardiogram; ECOG, Eastern Cooperative Oncology Group; LDH, lactate dehydrogenase; LVEF, left ventricular ejection fraction; MRI, magnetic resonance imaging; NCI-CTCAE, National Cancer Institute Common Terminology Criteria for Adverse Events; PD, progressive disease; PK, pharmacokinetics; PS, performance status; RECIST, Response Evaluation Criteria In Solid Tumors; WBC, white blood cells.

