Study visit window	-	Within 2 days of pre-specified date						±1 week			
Written informed consent	Before any study procedure	-	-	-	-	-	-	-			
Medical history	D-28 to D1	-	-	-	-	-	-	-			
Complete physical examination (2)	D-28 to D1	•	Repeat if clinically indicated				•	•			
ECOG-PS(2)	D-28 to D1	•	Repeat if clinically indicated				•	•			
Vital signs (2, 3)	D-28 to D1	•	•	•	-	•	•	•			
Weight, height and BSA	D-28 to D1	•	Repeat if clinically indicated			•	Repeat if clinically indicated				
Hematology (4)	D-7 to D1	•	•	•	-	•	•	•			
Biochemistry A (4, 5)	D-7 to D1	•	•	•	-	•	•	•			
Biochemistry B (6)	D-7 to D1	•	Repeat if clinically indicated			•	•	•			
Calculated creatinine clearance (6)	D-7 to D1	•	Repeat if clinically indicated			•	Repeat if clinically indicated				
Pregnancy test (7)	D-14 to D1	Every 4 weeks during treatment and 3 months after last dose administration									
ECG (5, 8)	D-28 to D1	Before each Zalypsis® infusion					•	•			
LVEF (ECHO) (5, 9)	D-28 to D1	Every other cycle					•	•			
Concomitant diseases and treatments	D-28 to D1	Throughout the “on-treatment” period						•			
Adverse events	NA	Throughout the “on-treatment” period						•			
Tumor assessment (10)	D-28 to D1	Every other cycle (± 1 week) until PD					•	•			
Pharmacokinetics (11)	D1	•	•	-	-	-	-	-			
Pharmacodynamic and pharmacogenomic samples, if patient consented (12, 13)	D-28 to D1	•	-	-	-	•	-	-			
Other tests	D-28 to D1	When indicated, according to the clinical and laboratory context					•	•			

See notes on next page →

SCHEDULE OF ASSESSMENTS AND PROCEDURES (CONTINUED)

On-treatment period = from first infusion of Zalypsis® to End of treatment.

End of treatment = 30 days after the day of last dose of study drug administration, unless the patient starts a new antitumor therapy or dies (whichever occurs first), in which case the date of administration of this new therapy or the date of death will be considered the date of end of treatment.

1. Patients withdrawn with Zalypsis®-related ongoing adverse events (AEs) must be followed up with the appropriate tests until event resolution.
2. Complete physical examination, ECOG PS, vital signs, and weight must be repeated on Day 1 of Cycle 1, prior to administration of the first Zalypsis® infusion.
3. Before any Zalypsis® infusion.

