3. OVERALL STUDY DESIGN

This is a multicenter, open-label, single-arm, non-comparative, phase II clinical trial with single-agent Zalyps[®] given as a 1-h i.v. infusion on d1, d8 and d15, q4wk, to patients with advanced and/or metastatic EFT who failed to standard chemotherapy.

The primary endpoint of the study is the overall response rate (ORR), defined as the percentage of patients with objective response (OR), either complete response (CR) or partial response (PR), as defined by the Response Evaluation Criteria in Solid Tumors (RECIST) v1.1.

The study will consist of two stages. If in the first stage there are no responders after testing the drug on 12 evaluable patients, the trial will be terminated. If there are ≥ 1 responders the trial will go on to the second stage and 17 additional evaluable patients will be accrued. A total of 29 evaluable patients will be studied. If the total number of responders is ≤ 2 , the drug will be considered as not interesting in the setting of patients treated for this disease with this schedule.

Treatment will be administered in the absence of disease progression and/or unacceptable toxicity. In case of obtaining a CR, two additional cycles will be administered and then the treatment will be stopped.

A disease evaluation will be performed at baseline and every other cycle (± 1 week) until evidence of disease progression.

Patients will be evaluated using clinical and laboratory assessments before and after each treatment cycle. Any treatment-related AEs will be followed-up until the events or their sequelae resolve or stabilize at a level acceptable to the Investigator and the Sponsor(s). Patients no longer receiving study treatment will be followed up for survival (see Section [5.2](#)).

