5.8. EVALUATION AT END OF TREATMENT

The end-of-treatment visit will be scheduled at 30 days after the last Zalypsis® infusion (a window of \pm 2 days is allowed).

Regardless of the reason for the discontinuation, the same complete workup conducted before study entry (except for medical history) will have to be done at this end-of-treatment visit. This will include the following assessments:

- Complete physical examination.
- Vital signs.
- ECOG PS.
- Weight and BSA, if clinically indicated.
- Hematology.
- Biochemistry A.
- Biochemistry B.
- Calculated creatinine clearance, if clinically indicated.
- Pregnancy test, if applicable.
- ECG and LVEF by ECHO.

- Concomitant diseases and treatments.
- Safety assessment (AEs).
- Tumor assessment.
- Other tests (when indicated, according to the clinical and laboratory context).

Adverse events must be reported until 30 days after the last study drug administration. All serious adverse events (SAEs) occurring within 30 days of the last study drug administration will be reported. Beyond this period of time, only those SAEs suspected to be treatment-related will be reported (see Section [9](#)).

The Sponsor(s) will evaluate all safety information that is spontaneously reported by an Investigator beyond the time frame specified in the protocol.

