7.4.6. Other safety evaluations

Physical examination evaluation (normal/abnormal) and vital signs at baseline and during treatment will be described by means of frequency counts and summary statistics.

Electrocardiogram (ECG) evaluation (normal/abnormal) will be summarized with frequency counts

Continuous variables (LVEF and LVEF Normal Range) will be summarized and presented with summary statistics, i.e., mean, standard deviation, median and range.

Tabulation of baseline values and evolution during treatment will be presented for PS, weight, and LVEF, troponin I measurement.

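### From Cycle 2 until the end-of-treatment visit, ECOG performance status and physical examination are recorded only on clinical indication, yet the SAP tabulates performance status by cycle and counts examination findings on treatment, with no denominator or missing-value rule

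*Protocol*

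**What the plan says.** Table 6 in Protocol section 5.7 puts complete physical examination and ECOG PS in one row, timed at "Day 1 of Cycle 1 prior to the Zalypsis® infusion, and then whenever clinically indicated". In the schedule of assessments in the synopsis, both rows have a mark at D1. The entry "Repeat if clinically indicated" then spans the columns up to and including D28, which is labelled as Day 1 of the next cycle. Footnote 2 to the schedule ties the compulsory repeat to the first cycle: these items "must be repeated on Day 1 of Cycle 1, prior to administration of the first Zalypsis® infusion".

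Other items are treated differently. For weight and body surface area, Table 6 says "Repeat on Day 1 of each cycle prior to the Zalypsis® infusion, and then whenever clinically indicated", and the weight row of the schedule has its own mark at D28. Vital signs and ECG are due before every infusion, and hematology and Biochemistry A on Days 1, 8 and 15.

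Both assessments become compulsory again at the end. Protocol section 5.8 says that "the same complete workup conducted before study entry (except for medical history) will have to be done at this end-of-treatment visit", and its list names both. Section 5.9 lists both at the three-monthly follow-up visits.

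On the analysis side, SAP section 7.4.6 states: "Tabulation of baseline values and evolution during treatment will be presented for PS, weight, and LVEF, troponin I measurement". It also states: "Physical examination evaluation (normal/abnormal) and vital signs at baseline and during treatment will be described by means of frequency counts and summary statistics". The shell of SAP Table 12.4.1 has a PS row under Baseline, Cycle 1, Cycle 2 and so on to Cycle (X).

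**The concern.** The SAP handles PS as if it were a scheduled measurement, in the same table as weight and blood pressure. From Cycle 2 on it is not one. Under the protocol as written, a PS value exists in those cycles only if someone saw a reason to take it, and the reason will often be that the patient looked worse. Such values are informatively missing. A by-cycle column built from them reads as the course of the cohort, but it describes the patients who prompted an assessment.

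The numbers are small: 29 evaluable patients if both stages are completed, and fewer in each later cycle. A few selective entries could dominate a column, and the shell does not tell the reader how many patients it rests on. Values that were never taken cannot be recovered at analysis.

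**Working it through.** The plan states no figure on this point, so there is none to reproduce. The check compares the two documents and then illustrates how large the selection could be.

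**Step 1: what is collected and what is tabulated.**

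| Time | PS and examination collected? | SAP output |
|---|---|---|
| Baseline | Yes, required | PS column in Table 12.4.1; both in Table 11.1.5.1 |
| Cycle 1, Day 1 | Yes, required | PS column for Cycle 1 |
| Cycle 2 to last cycle | Only on clinical indication | PS column for each cycle; examination within the on-treatment counts |
| End-of-treatment visit | Yes, required | No column in Table 12.4.1 |

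The mismatch lies in the third row. For PS it affects a named by-cycle table. For physical examination it affects only the on-treatment counts promised in SAP 7.4.6, because the only examination shell is the baseline one.

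**Step 2: is there a rule for the gaps?** SAP section 8.1 removes cycles with missing data from table denominators, but only for laboratory values and adverse events. Table 12.4.1 has no column for the number assessed. No rule covers PS or physical examination.

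**Step 3: how much could selection matter?** Let w be the true share of patients who are worse in a cycle, a the chance that PS is recorded if worse, and b the chance that it is recorded if not worse. All three are assumptions.

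- Share of patients with a recorded value = w·a + (1 − w)·b
- Share of recorded values that are worse = w·a / [w·a + (1 − w)·b]

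With w = 0.20 and a = 0.90, w·a = 0.18:

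| b | Share recorded | Worse among recorded |
|---|---|---|
| 0.50 | 0.18 + 0.40 = 0.58 | 0.18/0.58 = 31% |
| 0.20 | 0.18 + 0.16 = 0.34 | 0.18/0.34 = 53% |
| 0.10 | 0.18 + 0.08 = 0.26 | 0.18/0.26 = 69% |

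If everyone were recorded (a = b = 1), the table would show the true 20%. Varying w from 0.10 to 0.40 over the same values of b, the result runs from 0.09/0.54 = 17% to 0.36/0.42 = 86%. Whenever a exceeds b, the recorded share exceeds w. By how much depends almost entirely on b, which the documents do not give.

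**The case against.** Several points on the other side have weight.

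- **The end-of-treatment visit.** A reader might infer that neither assessment is ever required after Cycle 1 Day 1. That is wrong. Both are required at end of treatment whatever the reason for stopping, that visit falls within the on-treatment period as the protocol defines it, and both are listed at follow-up. Patients who attend therefore have a scheduled, unselected post-baseline value. This narrows the gap to Cycle 2 until end of treatment but does not close it: the visit is 30 days after the last infusion and has no column in Table 12.4.1.
- **Direction and size.** A reader might also infer that the recorded values would be mostly worse. The documents do not show this. Sites may record PS routinely, and under the assumptions above worse values pass one half only in some settings.
- **Physical examination by cycle.** No such table is planned, so the by-cycle criticism applies to PS alone.
- **The schedule header.** The D1 mark stands under a heading that covers Cycle 1 and further cycles, so it could be read as Day 1 of every cycle. Table 6, footnote 2 and the span through D28 all point the other way. At best this is an ambiguity that needs settling.
- **The listing fallback.** The SAP's note on table shells allows listings when a table would be too sparse, and a PS listing is planned. That helps presentation but sets no denominator and does not mark values as indication-triggered.
- **Protocol section 3.** It says "Patients will be evaluated using clinical and laboratory assessments before and after each treatment cycle". A reader might take this as a contradiction of Table 6. It names neither PS nor physical examination, and the scheduled vital signs, ECG and laboratory tests can satisfy it.
- **Clinical deterioration.** A reader might link irregular PS to the category of patients withdrawn for deterioration of unknown reason, who are replaced. No text ties that category to PS, and deterioration is when an indication-triggered PS is most likely to be taken.

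**Conclusion.** The mismatch between protocol and SAP is real and limited. Following both documents as written would fill the PS columns from Cycle 2 on, and part of the on-treatment examination counts, with values that exist only because someone judged an assessment necessary. Over-representation of worsening is probable. It rests on the assumption that worse patients are more likely to be assessed, and its size cannot be determined from the documents; the percentages above are illustrations, not estimates.

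The consequences stay within descriptive safety tables. PS enters neither the response rate, the two-stage rule, the re-treatment criteria nor any time-to-event endpoint, and adverse events are collected throughout treatment. The point is still worth correcting, because the remedy is cheap and the data cannot be reconstructed later.

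**What to change.** Preferred: in Protocol Table 6, require ECOG PS on Day 1 of every cycle before the infusion, and physical examination as well so that the on-treatment counts have a defined basis. Put the matching mark under D28 (Day 1 of the next cycle) in the schedule and bring footnote 2 into line. Build the PS row of SAP Table 12.4.1 from these Day 1 values and add the number assessed per cycle. The cost is a protocol wording change and a few minutes at a visit that already takes place for infusion, weight, vital signs, ECG and blood tests.

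If the protocol is not changed, close the gap in the SAP alone. Summarize PS and physical examination at baseline, Cycle 1 Day 1 and end of treatment only. List any other values separately, labelled as indication-triggered, with the number of patients assessed. This costs almost nothing, but it gives up a by-cycle description of PS.

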5.8. EVALUATION AT END OF TREATMENT

The end-of-treatment visit will be scheduled at 30 days after the last Zalypsis® infusion (a window of \pm 2 days is allowed).

Regardless of the reason for the discontinuation, the same complete workup conducted before study entry (except for medical history) will have to be done at this end-of-treatment visit. This will include the following assessments:

- Complete physical examination.
- Vital signs.
- ECOG PS.
- Weight and BSA, if clinically indicated.
- Hematology.
- Biochemistry A.
- Biochemistry B.
- Calculated creatinine clearance, if clinically indicated.
- Pregnancy test, if applicable.
- ECG and LVEF by ECHO.

- Concomitant diseases and treatments.
- Safety assessment (AEs).
- Tumor assessment.
- Other tests (when indicated, according to the clinical and laboratory context).

Adverse events must be reported until 30 days after the last study drug administration. All serious adverse events (SAEs) occurring within 30 days of the last study drug administration will be reported. Beyond this period of time, only those SAEs suspected to be treatment-related will be reported (see Section [9](#)).

The Sponsor(s) will evaluate all safety information that is spontaneously reported by an Investigator beyond the time frame specified in the protocol.

5.9. FOLLOW-UP AFTER END-OF-TREATMENT VISIT

The date and reason of the study discontinuation will be recorded on the patient's CRF (see Section [5.2.1.1](#)).

Patients who discontinue treatment without progression will be followed every three months until disease progression, other antitumor therapy or death or until the date of study termination, whichever occurs first. After disease progression or after other antitumor therapy, patients will be followed every three months until death, or until the date of study termination, whichever occurs first.

Patients' follow-up determinations will include: ECOG PS, vital signs, complete physical examination, weight if clinically indicated, hematology, biochemistry A and B, concomitant diseases and treatment, calculated creatinine clearance if clinically indicated, and tumor assessment.

Follow-up of cardiac assessments (including ECG and LVEF) should be performed at three and six months after end of treatment.

Patients who withdraw consent will not be followed with any study procedures.

Patients withdrawn with ongoing Zalyps[®]-related AEs (including SAEs) will be followed-up until the events or their sequelae resolve or stabilize at a level acceptable to the Investigator and the Sponsor(s).

Additional parameters will be assessed and/or the frequency of observations will be increased at the Investigator's discretion and according to the nature of the observed AEs. In case of death, when available, autopsy data should be provided.

6. PHARMACOKINETICS

All patients included in this study will be sampled for PK during the first two infusions of the first cycle. Blood samples for the measurement of the Zalyps[®] plasma concentration will be obtained following the sampling schedule detailed in [Table 7](#).

6.1. SAMPLE COLLECTION, STORAGE, AND SHIPPING OF THE PK SAMPLES

All PK sample collection dates and times will be recorded on the PK sheet.

In the treatment infusions with plasma sampling for PK, the infusion rate will be established so as to ensure that the total dose is infused in 1 hour. The drug will be infused at a constant rate throughout the 1-hour period. In order to obtain reliable PK information, the infusion rate should not be modified once it has begun. **If a variation in the infusion time occurred, it must be recorded on the CRF and PK sheet**, stating

clearly the time of the beginning and the end of the infusion. The infusion rate should not be changed to maintain the intended duration of infusion. It would be enough to record the actual duration on the CRF and on the PK sampling sheet for those cycles in which PK sampling is performed.

Blood samples for PK analysis will be obtained through a peripheral vein located in the contralateral side to the study drug infusion. **No sample (even the last one) must ever be collected from the catheter employed to administer Zalyps[®]**. If a blood sample is obtained from another catheter, the first milliliter (ml) of blood will be discarded to avoid dilution of the sample with the solution used to keep it permeable.

Five-ml blood samples will be collected in sodium heparin tubes. Sample tubes will be gently inverted several times to ensure adequate mixing and immediately centrifuged at 2500 x g for 15 min at +4°C to separate the plasma. If immediate centrifugation is not possible, the tubes containing the blood samples must be placed in an ice bath at 0-4°C for a maximum of 30 minutes. After centrifugation, the plasma will be transferred to the provided polypropylene tubes (one per sample) and stored at -20°C until shipped to the analysis laboratory. The cell pellet should be discarded. Blood and plasma tubes will be provided by the Sponsor(s).

Blood samples will be collected on Day 1 and 8 of Cycle 1, at the time points shown in [Table 7](#).

Table 7. Plasma pharmacokinetic sampling schedule

Sample number	Optimal time point	Adequate time frame
1	Pre-SOI	Pre-SOI
2	5 min before EOI	5-1 min before EOI
3	30 min after EOI	30 min-1 h after EOI
4	2 h after EOI	1.5-3 h after EOI
5	6 h after EOI	6-8 h after EOI
6	24 h after EOI	20-28 h after EOI
7	48 h after EOI	40-72 h after EOI
8*	168 h after EOI	120-168 h after EOI

*Sample number 8 has to be taken BEFORE the start of the next infusion.
SOI, start of infusion; EOI, end of infusion.

The accurate recording of actual dosing and sampling times is much more important than the strict adherence to the scheduled times.

Once all PK samples from a patient have been collected, they should be shipped to the central laboratory for PK analyses as soon as possible, ideally the next shipping day. The time span between the moment when the last PK sample for a patient has been collected and the shipment to the central laboratory of all samples from this patient should not exceed two months.

Samples will be sent for analysis in the boxes provided for this purpose, filled with dry ice, by the study courier service to the following address:

*[name]
Icon Development Solutions
Manchester Bioanalytical Laboratory
[name]
[name]
Manchester
[name]*

Samples will be identified with the following data: study reference, patient number, sample number, date and time of collection. At all times, the confidentiality of patient's data will be maintained.

Samples will be destroyed following the appropriate laboratory procedures, after the approval of the final analytical study report by the Sponsor(s).

A manual of instructions for sample collection, labeling, storage, and shipment will be provided (Instruction Manual for the Collection, Labeling, Storage and Shipment of Pharmacokinetic Samples).

